#### 5.5.1.1 Plasma Concentration Analysis

<Concentration>

Plasma concentrations of tazemetostat will be summarized using summary statistics (n, mean, SD, median, min and max) by timepoint in all subjects and subjects who collected blood sample for PK analysis within 8 to 16 hours after study drug administrationon respectively.

Plasma concentrations of tazemetostat will be listed for each subject by actual sampling time.

### 5.5.2 Pharmacodynamic, Pharmacogenomic, and Other Biomarker Analyses

This analysis will be performed on the Biomarker Analysis Set. Calculate frequency and rate of the tumor EZH2 gene mutation in each disease.

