9.1.1.1 Pre-treatment Phase

The Pre-treatment Phase consists of Screening 1, Screening 2, registration, and baseline assessment. In Screening 1, the EZH2 gene mutation will be confirmed at central laboratory in patients with histologically diagnosed as FL (cohort 1) or DLBCL (cohort 2) who are available to provide archival tumor sample (Inclusion Criteria 1) and not apparent to conflict other eligible criteria to participate in the study. The archival tumor samples will be submitted to the central laboratory, and then this will be reported to the sponsor. If EZH2 gene mutation was confirmed, conduct Screening 2 to confirm the other eligibility for study treatment. Obtain the written informed consent with regards to tumor EZH2 gene mutation test and study treatment respectively, before Screening 1 and Screening 2. Screening 2 will last no longer than 28 days before the start of study treatment. After screening assessments, the patient who meets the inclusion criteria and does not meet the exclusion criteria will be enrolled. The baseline assessment will be conducted within 3 days before the treatment in order to confirm that the patient continues to meet the inclusion criteria and does not meet the exclusion criteria before moving to the Treatment Phase.

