9.3.1 Inclusion Criteria

Subjects must meet all of the following criteria to be included in this study:

- (1) Patient with histological diagnosis of B-cell NHL as follows, who has provided written consent to submit archival tumor sample to central laboratory to confirm the EZH2 gene mutation status in tumor:
 - · Cohort 1: Follicular lymphoma (FL)
 - · Cohort 2: Diffuse large B-cell lymphoma (DLBCL) (including primary mediastinal B-cell lymphoma and transformed FL)
- (2) Patient who has confirmed EZH2 gene mutation of tumor in central laboratory
- (3) Patient who has measurable disease as below:
 - · Lymph node or ex-nodal disease diagnosed by CT scan
 - · Clearly measurable in 2 orthogonal ways by CT scan
 - $\cdot \ge 1.5$ cm in long axis or >1.0 cm in short axis, when long axis were <1.5 cm
- (4) Patient who had previous therapy with systemic chemotherapy and/or antibody therapy and for which no standard therapy exists
- (5) Patient who was progressive disease (PD) or did not have response (complete response [CR] or partial response [PR]) in previous systemic therapy, or relapsed or progressed after previous systemic therapy
- (6) Patient with Eastern Cooperative Oncology Group (ECOG) performance status of 0 to 1
- (7) Patient with life expectancy of ≥ 3 months from starting study drug administration
- (8) Patient with adequate renal function:
 - · Serum creatinine ≤1.5× upper limit of normal (ULN)
- (9) Patient with adequate liver function:
 - · Total bilirubin <1.5×ULN
 - · Aspartate aminotransferase (AST) and alanine aminotransferase (ALT) \(\leq 3.0 \times ULN \)
- (10) Patient with adequate bone marrow function:

(confirm 2 weeks or later from last administration of granulocyte colony-stimulating factor [G-CSF] and blood transfusion, if these are used)

- · Absolute neutrophil count $\ge 1.5 \times 10^3 / \mu L (\ge 1.5 \times 10^9 / L)$
- · Platelet count $\geq 10.0 \times 10^4/\mu L$
- · Hemoglobin ≥9.0 g/dL
- (11) Patient with time between prior anti-tumor therapy and first administration of study drug as below:
 - · Cytotoxic chemotherapy At least 3 weeks
 - · Non-cytotoxic chemotherapy (eg, corticosteroids*, small molecule inhibitor) At least 2weeks
 - · Monoclonal antibody (ies) At least 4 weeks

Eisai Confidential Page 33 of 71 FINAL: 29 Jan 2021

- · Radiotherapy
 - -At least 3 weeks from radiation therapy
 - -At least 6 weeks from prior radioisotope therapy
- · Autologous hematopoietic stem cell transplantation At least 6 months

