9.5 Study Assessments

9.5.1 Assessments

9.5.1.1 Demography

Subject demography information will be collected and noted on the CRF. The information to be collected at Screening 1 includes Subject ID Number, date of written informed consent for tumor EZH2 gene mutation test, date of birth (or age), sex, race, ethnicity, primary disease (date of diagnosis, disease diagnosis [see below]), and EZH2 gene mutation status (including known information of EZH2 gene mutation status, sampling date of tissues). The information to be collected at Screening 2 includes date of written informed consent for study treatment, clinical staging, B symptoms, prior therapies for primary disease.

(1) Primary disease

- Date of diagnosis
- Disease diagnosis (for DLBCL only: Cell-of-origin [COO] and test method)
- Clinical staging at Screening (Ann Arbor staging) (Carbone, et al., 1971)
- B symptoms (unexplained fever more than 38 °C, drenching night sweats, unexplained weight loss of more than 10% of usual body weight over 6 months)
- (2) Prior therapies for primary disease
 - 1) Chemotherapy (type of therapy, best overall response, name of therapy/drug, start dates, end dates)
 - 2) Radiotherapy (site of radiation, deterioration after radiotherapy, first date of radiation, last date of radiation)
 - 3) Autologous stem cell transplantation (with or without autologous stem cell transplantation, date of transplantation)

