9.7.1.7.2 PHARMACODYNAMIC, PHARMACOGENOMIC, AND OTHER BIOMARKER ANALYSES

This analysis will be performed on the Biomarker Analysis Set. The rate of the tumor EZH2 gene mutation will be calculated in each disease.

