##### 3.1.3 Exploratory Objectives

- (1) To explore the pharmacokinetics (PK) of tazemetostat.
- (2) To explore the frequency of EZH2 gene mutation in B-cell NHL.

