## 5.2 Study Subjects

### 5.2.1 Definitions of Analysis Sets

**Efficacy Analysis Set** will include efficacy evaluable subjects who received at least 1 administration of the study drug and who has appropriate tumor assessment data of Screening 2 and post-baseline.

**Pharmacokinetic Analysis Set** will include subjects who received at least 1 administration of the study drug and had at least 1 concentration data of tazemetostat.

**Biomarker Analysis Set** will include subjects who have conducted EZH2 gene mutation assessment at Screening 1.

**Safety Analysis Set** will include subjects who received at least 1 administration of the study drug.

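### Does the crude EZH2 mutation rate among all subjects tested at Screening 1 need a split by prior known status and cell of origin?

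*SAP*

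**What the plan says.** The objective is exploratory. SAP 3.1.3 words it as "To explore the frequency of EZH2 gene mutation in B-cell NHL".

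The analysis is one sentence in each document. SAP 5.5.2 has "Calculate frequency and rate of the tumor EZH2 gene mutation in each disease", and Protocol 9.7.1.7.2 has "The rate of the tumor EZH2 gene mutation will be calculated in each disease". The denominator is the Biomarker Analysis Set, which SAP 5.2.1 defines as "subjects who have conducted EZH2 gene mutation assessment at Screening 1". No confidence interval and no subdivision within a disease is specified.

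Two items that could describe the tested patients are collected. Protocol 9.5.1.1 lists, at Screening 1, "EZH2 gene mutation status (including known information of EZH2 gene mutation status, sampling date of tissues" and, under primary disease, "Disease diagnosis (for DLBCL only: Cell-of-origin [COO] and test method". Protocol 11.4 requires a case report form for everyone who consents to the mutation test. The SAP names cell of origin only in the baseline table of SAP 5.2.3, which covers the Safety and Efficacy Analysis Sets. It names prior known status in no analysis.

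**The concern.** Entry to treatment requires a positive test: Protocol 9.3.1, criterion 2, reads "Patient who has confirmed EZH2 gene mutation of tumor in central laboratory". A site holding a local result therefore has more reason to send a known positive than a known negative. Protocol 9.1.1.1 also restricts Screening 1 to patients described as "Inclusion Criteria 1) and not apparent to conflict other eligible criteria to participate in the study". If that phrase covers criterion 2, known negatives might never be tested centrally.

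DLBCL has a second route. Protocol 7.2.4 reports activating mutations in 22% of GCB cases and in none of the non-GCB cases, so the DLBCL rate depends on the mix of cell types tested. The baseline table cannot show that mix, because its subjects are treated and hence mutation-positive.

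At stake is whether the reported rate could be read as the frequency in the disease, or only as the frequency among those whom sites chose to refer.

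**Working it through.** **1. Is any rule or number wrong?** Set side by side, Protocol 9.7.1.7.2 and SAP 5.5.2 plan the same quantity, by disease, on the same set. Giving both frequency and rate supplies the count and the denominator, so a reader can compute an exact interval. Neither document states a target precision for this rate, so there is no planned figure to reproduce. The background estimates that use the mutation rates do reproduce:

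- DLBCL diagnosed (Protocol 7.2.1, 7.2.4): 64,000 × 45.3% × 50% × 22% = 3,189, stated as about 3,200.
- DLBCL, yearly figure: 26,600 × 45.3% × 50% × 22% = 1,325, stated as about 1,300.

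They imply a DLBCL rate of 50% × 22% = 11%. For FL, Protocol 7.2.2 gives 7% to 27%.

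**2. How large could referral selection be?** The documents give neither the share of candidates with a prior result nor the GCB share among those tested. Both are assumed here.

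*Prior-status route.* Let f be the true rate and s the share with known status. If every known negative is held back and all others are sent equally, the observed rate is f / (f + (1 − f)(1 − s)).

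| True rate f | s = 5% | s = 20% |
|---|---|---|
| 7% | 0.07/0.9535 = 7.3% | 0.07/0.814 = 8.6% |
| 11% | 0.11/0.9555 = 11.5% | 0.11/0.822 = 13.4% |
| 27% | 0.27/0.9635 = 28.0% | 0.27/0.854 = 31.6% |

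With equal referral the observed rate is f, and there is no bias.

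*Cell-of-origin route, DLBCL.* The observed rate is 22% × GCB share: 11.0% at a 50% share, 13.2% at 60%, 17.6% at 80%.

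*Scale.* If every positive patient enrolled, 13 DLBCL subjects at 11% imply 13/0.11 ≈ 118 tested. The exact 95% interval for 13/118 is 6.0% to 18.1%. Each DLBCL shift above, taken alone, lies within it.

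**3. Do the documents show the mechanism?** No section says that sites pre-tested EZH2, held back known negatives or favoured GCB cases. Criterion 2 is a central-laboratory result, and Screening 1 is the step that produces it (Protocol 9.1.1.1). A local negative is therefore not, as written, a conflict with criterion 2. Reading the Screening 1 condition to include the very criterion under test is strained.

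**4. Would the split recover the frequency in the disease?** Not reliably.

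- Suppose all prior-tested DLBCL cases were GCB. The unknown-status rate would be 22% × (0.5 − s)/(1 − s): 10.4% at s = 5% and 8.25% at s = 20%, both below 11%. A further split by cell of origin would remove that particular error, but at the price of smaller cells.
- Cohort 2 includes primary mediastinal lymphoma and transformed FL (Protocol 9.1), for which the documents give no mutation rate. The GCB formula leaves them out. If, as an assumption, 20% of those tested were transformed FL at 7% to 27% and the rest were at 11%, the rate would run from 0.2 × 7% + 0.8 × 11% = 10.2% to 0.2 × 27% + 0.8 × 11% = 14.2%, with no referral selection at all.
- Everyone at Screening 1 has archival tissue and no apparent conflict with the other entry criteria, such as relapsed or refractory disease. Any rate from this group describes trial candidates, with or without a split.

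**The case for a change.** The strongest case for acting is that the data are already collected, the table is cheap, and as planned a reader cannot separate disease from referral. A field for prior known status suggests that the sponsor expected some patients to arrive with a result. SAP 5.7 permits exploratory analyses but commits to none.

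Nor is the bias bounded by the examples above. If 10% of tested DLBCL subjects were already known positive and the rest were at 11%, the rate would be 10% + 90% × 11% = 19.9%. With an 80% GCB share, and with 20% known status and all negatives held back, it would be 0.176/(0.176 + 0.824 × 0.8) = 21.1%. Both lie outside 6.0% to 18.1%.

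These sums are correct, and it is true that the SAP text specifies no such split. The table shells are a separate document (SAP 11), so they cannot settle the matter either way. What stands is that a descriptive split and exact intervals would help a careful reader. But the figures show what assumed selection would do, not that selection occurred. The lack of an optional breakdown for an exploratory rate is a preference about output and does not make the planned rate wrong.

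Clarifying Protocol 9.1.1.1 would no longer help. The synopsis links the cut-off of 02 Dec 2020 to 24 months after the last enrolment, which puts that enrolment at about December 2018. The current protocol is dated 29 Jan 2021, so rewording it cannot change who was tested.

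**Conclusion.** The concern does not hold. The plan defines a descriptive mutation rate by disease, among all subjects tested, consistently in both documents and in keeping with an objective that only sets out to explore. The size of any referral bias is unknown. It is zero under equal referral, and each DLBCL shift in the main illustrations, taken alone, is within sampling error. Larger values need assumptions about prior testing or cell-type mix that the documents do not supply. The objective response rate, the secondary endpoints, safety and the sample sizes of 8 and 13 do not depend on this rate.

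The conclusion rests on reading the result as what it is: the rate among patients tested for this trial. It would need another look if the study records showed that many patients came with a prior EZH2 result and that referral followed it.

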## 5.6 Safety Analyses

All safety analyses will be performed on the Safety Analysis Set. All safety result will be summarized for each disease (cohort) and overall. Safety variables include AEs, clinical laboratory parameters, vital signs, weight, ECOG PS, and 12-lead ECGs results.

### 5.6.1 Extent of Exposure

The number of cycles received, duration of treatment, total dose per subject, dose intensity per subject, received dose as percentage of planned starting will be summarized for each disease (cohort) and overall. Number of subjects with dose reductions and dose interruptions will be summarized for each disease (cohort) and overall. As for the subjects with any dose reduction, time to first dose reduction will also be summarized.

The actual dosing transition and duration of both study drug with tumor response is presented using swimmer plot.

### 5.6.2 Adverse Events

The AE verbatim descriptions (investigator terms from the CRF) will be classified into standardized medical terminology using the Medical Dictionary for Regulatory Activities (MedDRA). AEs will be coded to the MedDRA (Version 22.0) lower level term (LLT) closest to the verbatim term. The linked MedDRA preferred term (PT) and primary system organ class (SOC) will also be captured in the database.

A treatment-emergent adverse event (TEAE) is defined as an AE that emerged during time from the first dose of study drug to 37 days after the subject's last dose, having been absent at pretreatment (Baseline) or

- Reemerged during treatment, having been present at pretreatment (Baseline) but stopped before treatment, or
- Worsened in severity during treatment relative to the pretreatment state, when the AE was continuous.

Only those AEs that are treatment emergent will be included in summary tables. All AEs, treatment emergent or otherwise, will be presented in subject data listings.

The number and percentage of subjects with TEAEs will be calculated from the following viewpoints.

- All/Treatment-related Treatment-Emergent Adverse Events by System Organ Class and Preferred Term
- All/Treatment-Emergent Adverse Events by Preferred Term in Decreasing Frequency
- All/Treatment-Emergent Adverse Events by System Organ Class, Preferred Term, and CTCAE Grade
- All/Treatment-Emergent Serious Adverse Events by System Organ Class, Preferred Term
- All/Treatment-Emergent Adverse Events Leading to Death by System Organ Class and Preferred Term
- All/Treatment-Emergent Adverse Events Leading to Study Drug Withdrawal by System

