9.5.1.5.1 ADVERSE EVENTS

An AE is any untoward medical occurrence in a patient. An AE does not necessarily have a causal relationship with the medicinal product. For this study, the study drug is tazemetostat.

The criteria for identifying AEs in this study are:

- Any unfavorable and unintended sign (including an abnormal laboratory finding), symptom, or disease found after the time of informed consent, whether or not considered related to the investigational product (Note: Every sign or symptom should not be listed as a separate AE if the applicable disease [diagnosis] is being reported as an AE)
- Any new disease or exacerbation of an existing disease. However, worsening of the primary disease should be captured under efficacy assessments as disease progression rather than as an AE.
- Any deterioration in protocol-required and nonprotocol-required measurements of a laboratory value or other clinical test (eg, ECG or x-ray) that results in symptoms, a change in treatment, or discontinuation of study drug
- Recurrence of an intermittent medical condition (eg, headache) not present pretreatment (Baseline)
- An abnormal laboratory test result should be considered an AE if the identified laboratory abnormality leads to any type of intervention, withdrawal of study drug, or withholding of study drug, whether prescribed in the protocol or not

All AEs, regardless of relationship to study drug or procedure, should be recorded beginning from the time the subject signs the study ICF through the final observation visit. When subject needs to receive other anti-tumor therapy within 30 days after the final study drug administration, final observation must be conducted before initiation of other anti-tumor therapy. SAEs will be collected until the final observation visit.

Any laboratory abnormality considered to constitute an AE should be reported on the CRF. Abnormal laboratory values should not be listed as separate AEs if they are considered to be part of the clinical syndrome that is being reported as an AE. It is the responsibility of the investigator or subinvestigator to review all laboratory findings in all subjects and determine if they constitute an AE. Medical and scientific judgment should be exercised in deciding whether an isolated laboratory abnormality should be classified as an AE.

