9.5.1.5.2 SERIOUS ADVERSE EVENTS AND EVENTS ASSOCIATED WITH SPECIAL SITUATIONS

An SAE is any untoward medical occurrence that at any dose:

• Results in death

Eisai Confidential Page 47 of 71

- Is life-threatening (ie, the subject was at immediate risk of death from the adverse event as it occurred; this does not include an event that, had it occurred in a more severe form or was allowed to continue, might have caused death)
- Requires inpatient hospitalization or prolongation of existing hospitalization
- Results in persistent or significant disability/incapacity
- Is a congenital anomaly/birth defect (in the child of a subject who was exposed to the study drug)

Other important medical events that may not be immediately life-threatening or result in death or hospitalization but, when based on appropriate medical judgment, may jeopardize the subject or may require intervention to prevent one of the outcomes in the definition of SAE listed above should also be considered SAEs. Medical and scientific judgment should be exercised in deciding whether expedited reporting is appropriate in such situations.

For this study, occurrence of T-cell lymphoblastic lymphoma/T-cell acute lymphoblastic leukemia or myeloid malignancy including myelodysplastic syndrome will be considered AEs of interest for this study. These events should be reported to the sponsor by completed SAE report (see Section 9.5.4.3.2) and considered as serious only if events meet the serious criteria. These AEs should be entered on the CRF even if the events do not meet serious criteria. If subject experiences T-cell lymphoblastic lymphoma/T-cell acute lymphoblastic leukemia, enrollment of subject should be discontinued.

In addition to the above, events associated with special situations include pregnancy or exposure to study drug through breastfeeding; AEs associated with study drug overdose, misuse, abuse, or medication error (see Sections 9.5.4.2 and 9.5.4.3). These events associated with special situations are to be captured using the SAE procedures but are to be considered as SAEs only if they meet one of the above criteria. All AEs associated with special situations are to be reported on the CRF whether or not they meet the criteria for SAEs.

All SAEs must be followed to resolution or, if resolution is unlikely, to stabilization.

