9.5.4.3.2 Reporting of Study-Specific Events

The occurrence of T-cell lymphoblastic lymphoma/T-cell acute lymphoblastic leukemia or myeloid malignancy including myelodysplastic syndrome will be considered events of interest for this study. These events should be directly reported to the sponsor as soon as possible (no later than 1 business day) after obtaining the information. In addition, these events should be directly reported to the sponsor or by fax with completed SAE report promptly. The faxed report should be followed up by the original SAE report. Events of interest for this study must be followed to resolution or, if resolution is unlikely, to stabilization. Any event of interest to be related to the study drug or any protocol-required procedure judged by the investigator or subinvestigator should be reported to the sponsor regardless of the length of time that has passed since study completion.

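### A related T-cell lymphoblastic or myeloid malignancy starting more than 37 days after last dose must be reported under the protocol, but it would enter no SAP summary table and its listing is not assured

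*SAP*

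**What the plan says.** **Events of interest.** Protocol 9.5.4.3.2: "The occurrence of T-cell lymphoblastic lymphoma/T-cell acute lymphoblastic leukemia or myeloid malignancy including myelodysplastic syndrome will be considered events of interest for this study". Protocol 9.5.1.5.2 says the same and also requires these events to be entered on the CRF even when not serious. It gives no end date for that entry.

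**Reporting.** Protocol 9.5.4.3.2 has no time limit for cases that the site physician considers related to tazemetostat or to a study procedure. Such a case "should be reported to the sponsor regardless of the length of time that has passed since study completion".

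**Routine recording.** Under Protocol 9.5.1.5.1, adverse events "should be recorded beginning from the time the subject signs the study ICF through the final observation visit". Protocol 9.1.1.3 sets that visit at 30 days (+7) after last dose, or at the start of new anti-tumour therapy if earlier, and waives it for subjects who move to commercial drug.

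**Tables.** SAP 5.6.2 counts an event as treatment-emergent if it "emerged during time from the first dose of study drug to 37 days after" the last dose, and adds: "Only those AEs that are treatment emergent will be included in summary tables". Protocol 9.7.1.8.2 has the same restriction to treatment-emergent events, without a day count. The synopsis (Safety Analyses) is wider: it promises summaries and listings of all AEs and SAEs after first dose and gives no end of window.

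**Listings.** SAP 5.6.2: "All AEs, treatment emergent or otherwise, will be presented in subject data listings".

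**The concern.** The sponsor has decided that late related cases of these malignancies matter and has arranged to receive them. The analysis plan does not carry that decision through. Its only rule for tables stops at day 37, and no table or listing is set aside for these events.

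Safety is a secondary objective, and in a study of about 21 patients a single case of a pre-named risk is itself the signal. A reader who works from the tables could see none while the sponsor holds a reported case. The issue is how the plan handles events that the trial does collect. It is not the length of routine adverse event follow-up.

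**Working it through.** **1. The plan's own figure.** The final observation falls at 30 days with a +7 day allowance (Protocol 9.1.1.3). 30 + 7 = 37 days, which is the limit in SAP 5.6.2. The window is therefore derived from the visit schedule, not chosen for these malignancies.

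**2. Tracing a related case that starts on day 60 after last dose.**

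| Step | Source | Outcome |
|---|---|---|
| Must it be reported? | Protocol 9.5.4.3.2 | Yes, no time limit if judged related |
| Is it treatment-emergent? | SAP 5.6.2 | No, 60 > 37 |
| Does it enter a planned AE table? | SAP 5.6.2 | No. Every table listed is a table of treatment-emergent events, including the post-approval one for the FL cohort |
| Is it on the CRF? | Protocol 9.5.1.5.1 and 9.5.1.5.2 | Not settled. General recording has ended; the specific instruction has no end date |
| Is it listed? | SAP 5.6.2 | Yes if on the CRF database; otherwise not assured |
| Is the safety database a source? | SAP | Not named; no reconciliation described |

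The same trace applies to any start date from day 38. For subjects who switch to commercial drug, follow-up of adverse events ends at the discontinuation visit (Protocol 9.5.1.5.1), so a later case depends wholly on the open-ended reporting duty.

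**3. Illustrative size.** Inputs: planned efficacy-evaluable numbers 8 and 13 (Protocol 9.7.2), 8 + 13 = 21. Using 21 for the Safety Analysis Set is an assumption. Exact (Clopper-Pearson) two-sided 95% limits are used throughout.

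- As tabulated, 0/21: upper limit = 1 − 0.025^(1/21) = 16.1%, so 0 to 16.1%.
- With the late case counted, 1/21 = 4.8%: lower limit = 1 − 0.975^(1/21) = 0.1%; the upper limit solves (1−p)^21 + 21p(1−p)^20 = 0.025, giving p = 23.8%.
- By cohort: 0/8 (0 to 36.9%) against 1/8 = 12.5% (0.3% to 52.7%); or 0/13 (0 to 24.7%) against 1/13 = 7.7% (0.2% to 36.0%).

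**4. How likely is a late case?** The documents give no rate. The chance of at least one in 21 subjects is 1 − (1−q)^21, where q is an assumed risk per subject:

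| q | Chance of at least one case |
|---|---|
| 0.5% | 10% |
| 1% | 19% |
| 2% | 35% |
| 5% | 66% |

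**The case against.** The strongest reply has four parts.

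- **Listings.** SAP 5.6.2 puts all adverse events in listings, treatment-emergent or not, and Protocol 9.7.1.8.2 promises listings of all SAEs. With about 21 patients, a listing shows a single case plainly. This stands for any case on the CRF database. It does not help a case known only from an SAE report, and the documents leave that possibility open.
- **No breach by the SAP.** Protocol 9.7.1.8.2 has the same treatment-emergent rule, and 37 days matches the final visit. This stands. The gap lies between reporting and analysis. The wider wording is in the synopsis, and SAP section 7, which lists changes from the protocol, does not mention the 37-day limit.
- **Cases inside the window are covered.** They appear in the tables by system organ class, preferred term and grade. This stands: what is missing is a dedicated output and any place in the tables for late cases.
- **Reporting is not incidence.** A duty to report without time limit, confined to cases judged related, does not imply an incidence table without time limit. No active follow-up supports a rate. This stands too, and it shapes the fix.

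A reader might infer that a late case would vanish from all safety output, or that the safety conclusion would be wrong. The documents support neither. A listing is available, and a table labelled treatment-emergent that shows no case would be correct as labelled.

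**Conclusion.** The gap is real but limited. By a stated rule, a related T-cell lymphoblastic or myeloid malignancy that starts on day 38 or later would be left out of every adverse event summary table. Whether it would be listed depends on CRF entry after the final observation, which the protocol does not settle, and the SAP has no safety-database source as a backstop.

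One late case would change the tabulated result from 0/21 to 1/21, or from 0% to 4.8%. The two intervals overlap heavily, so the loss is the case itself, not a precise rate. This rests on the planned 21 evaluable patients standing in for treated subjects, and on a hypothetical case. A reader might set the one-sided 95% upper bound for 0/21, 1 − 0.05^(1/21) = 13.3%, beside the two-sided upper limit of 23.8% for 1/21. That would exaggerate the contrast; the like-for-like limit for 0/21 is 16.1%.

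The plan should be changed, because the correction is cheap and bears directly on the risk that the protocol itself names.

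**What to change.** In SAP 5.6.2, add an exception to the treatment-emergent-only rule:

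- a count and a listing of T-cell lymphoblastic lymphoma/leukaemia and myeloid malignancy (including myelodysplastic syndrome) in the Safety Analysis Set, by cohort and overall, from first dose to database lock;
- source: the CRF reconciled with the SAE/safety database;
- for each case, time from first dose and from last dose, with a flag for those outside the treatment-emergent window;
- a footnote that late cases are passively reported and that the open-ended duty covers only those judged related, so the count is not an incidence rate;
- cases reported after lock described in narratives.

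Record the exception in SAP section 7, and align the synopsis wording with Protocol 9.7.1.8.2.

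Cost: one small table, one listing and one reconciliation before lock. No new data collection is needed. The drawback is a count with no defined observation time, which the footnote must make clear.
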